2. Recruitment. We will recruit participants through posted flyers, e-mail, electronic and newsprint advertisements (e.g. campus student and faculty/staff newspapers, local and regional newspapers; see attachment “*Advertisements*”), and word of mouth. The posted advertisements will instruct interested participants to call the study center ([name] Laboratory, Department of Human Sciences) or complete an online pre-screening survey to obtain further information. During the phone-in hours, a trained individual (i.e. project coordinator or graduate assistant) will be available to describe the study and determine preliminary qualification by conducting a scripted phone interview (e.g. do you take dietary supplements?, do you smoke?; see “*Phone Script*” attachment). The individual will record answers and assess whether the person calling is likely or not to be an acceptable study participant. If the caller and the interviewer agree that the caller should participate, the prospective participant will be invited to a screening meeting, where the study will be fully described, and the individual will be provided a consent form to complete prior to any involvement in the study procedures. Data collected during this phase will include participant’s age, health status, physical activity, and contact information (see “*Informed Consent*” attachment).

3. Power Calculation and Data Analysis. [name] (biostatistician; *co-PI and Dept of Biomedical Informatics*) performed a power analysis. To ensure that the order by which each participant completes each trial is randomized, a random sequence generator (<http://www.random.org/sequences/>) will be used to determine the order by which each participant will undergo the two trials. We will primarily compare the

within-subject changes (WWB endpoint vs. WB endpoint) between high-responders and low-responders. We anticipate to have 6-12 high-responders and 5-10 low-responders of the total 40 study participants to achieve 80% power to detect a 1.6-fold difference in the changes of postprandial glucose levels (AUC from 0 to 180 minutes) between high-responders and low-responders, at the expected coefficient of variation (CV) 0.5 at a significant level of 0.05.

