2. Screening Meeting. Potential participants who have met the initial criteria of the study (based on the telephone interview) will be invited to the study center at a mutually convenient time. During this time, the participant and a member of the research team will meet in a private, quiet conference room or office. The individual will be provided the informed consent form, and its contents will be described to the potential participant. The participant will then review it, and if they choose to participate in the study, they will be asked to provide written consent. Although the participant will be asked to sign the informed consent, the participant will be told that they will not be asked to participate if their body measurements or plasma chemistries (see *Enrollment Criteria*) do not meet the study criteria. If the participant has provided consent, we will then measure the participant's height, weight, and blood pressure. Next, if the participant is fasted for at least 10 hours, we will ask if a trained individual can draw a small blood sample (10 mL; 2 tubes) so that we may measure blood chemistries (glucose, total and HDL-cholesterol, triglyceride). All samples will be coded to maintain participant anonymity. If the participant's anthropometrics or plasma chemistries do not meet the study criteria, they will be told that they do not meet the study criteria.

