 - *Day 10:* Participant will visit the study center briefly to pick-up meals that will be consumed on Days 11-14. Participant will return all uneaten foods and containers to the study team to determine actual food consumption during the preceding period. A stool collection kit will also be provided.
 - *Day 14:* Participant will visit the study center in the fasting state. The participant will provide a fecal sample that was self-collected during the preceding 24-hours. A urine sample will be collected to assess compliance to test meals. Participant will also return all uneaten foods and containers to the study team to determine actual food consumption during the preceding period. Anthropometrics and blood pressure will be assessed. Blood will be collected (0 min) and then an oral glucose tolerance test (75 g) and gut permeability test as described.⁵⁹ will be completed simultaneously. After emptying their bladder, the participant will ingest a 75 g glucose solution containing non-digestible sugars. Blood samples will be collected at 30-min intervals for 3-hours. Participant will be provided urine collection containers to self-collect urine for the subsequent 24-hours. During this 24-hour period, participants will also be provided controlled meals and beverages.
 - *Day 15:* Participant will return to the study center to provide collected urine. All procedures for Trial 1 are deemed complete.
- **Wash-out Period.**

Trial 1 and Trial 2 will be separated by at least two-weeks for men. However, the washout period for women may be extended to enable testing during the same phase (\pm 3 days) of the menstrual cycle.

- **Trial 2 Procedures (2-week intervention to WWB or WB).**

All procedures for Trial 2 will be identical to those of Trial 1 with the exception that the participant will receive the alternative test meals. If the participant was assigned WWB in Trial 1, WB will be assigned in Trial 2. If WB was assigned in Trial 1, then WWB will be provided in Trial 2.

- **Study Completion**

On Day 16 of Trial 2, the participant's involvement in the entire study is completed. A check will be provided to the participant in accordance with the payment schedule (up to \$350) that is outlined in the consent form.

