During each blood collection, plasma will be obtained by centrifugation and then transferred to cryogenic storage tubes. Serum samples will be obtained by allowing the blood to clot, followed by centrifugation and transfer to cryogenic storage tubes. Tubes will be stored at -80° C until analysis can be completed. Analyses will include plasma glucose, insulin, triglyceride, HDL cholesterol, proinflammatory genes and/or proteins (e.g., TLR4, CD14, MD2, MyD88, p65, IL-1, IL-6, IL-8, TNF- α , MCP-1), and serum endotoxin. Urine will be stored at -80°C until analysis can be completed. Analysis from urine will include sucralose, erythritol, lactulose, and mannitol. Fecal samples will be stored at -80°C until analysis can be completed. Feces analysis will include microbiota composition, calprotectin, myeloperoxidase (MPO), and fecal metabolomics analysis. Remaining plasma, serum, urine, and fecal samples not used for these analyses will be archived for 5 years at -80 C in the event we decide to measure additional biomarkers. Appropriate notation has been made in the informed consent to alert participants that we will be archiving specimens and that they have the right to refuse our use of these specimens for future analyses. Lastly, approval from OSU IRB will be sought via a protocol amendment prior to the analysis of any additional biomarkers not specified herein.

E. Privacy/Confidentiality

For all data and records that are a part of this study, a number (i.e. code) will be assigned to each participant and will only be available to research personnel. Any records containing the names of participants will be stored in a locked filing cabinet or on a password protected computer in the PI's laboratory or office.

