Research personnel under the supervision of the PI and the PI himself will be the only individuals that have access to this information. The names of participants will not be used for publication in any form. The records will be maintained until the data are published, up to a maximum of five years. All archived samples will be coded, but the key linking the code to each participant's identifiable information will have been destroyed. In addition, participants will be instructed that their participation in this study is voluntary and that they may withdraw at any time without prejudice. Data (biochemical values) obtained from this study will be stored on a computer in the PI's laboratory. In addition, a backup of digital data will be stored on the PI's computer in his office. Both computers are password protected and both doors are locked when work areas are not in use.

F. Internal Validity

For all data and records that are a part of this study, a number (i.e. code) will be assigned to each participant. This will minimize measurement bias when performing analysis on dietary records, and biochemical markers because all samples/records will be coded. The codes will only be broken once data analysis has been completed and verified by the PI.

G. Medical Safety Plan

All aspects of the clinical study will be conducted in [name] clinical lab located in [name]. Participants will be fasted for 10-12 hours prior to each study visit. We recognize that certain risks associated with fasting include: hypoglycemia, weakness, and fainting. This duration of fasting is consistent with guidelines set forth by the American Diabetes Association to minimize risk to the individual⁶² when determining fasting blood glucose concentrations.

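### The participant code in VI.F identifies the person, not the bread, so the claimed protection against measurement bias is not established

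*Combined protocol and SAP*

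**What the plan says.** VI.F (Internal Validity) describes one measure: "a number (i.e. code) will be assigned to each participant". It draws a bias claim from it: "This will minimize measurement bias when performing analysis on dietary records, and biochemical markers because all samples/records will be coded". It then adds: "The codes will only be broken once data analysis has been completed and verified by the PI".

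VI.E (Privacy/Confidentiality) describes the same measure in almost the same words: "a number (i.e. code) will be assigned to each participant and will only be available to research personnel". On records that carry names, it says: "Research personnel under the supervision of the PI and the PI himself will be the only individuals that have access to this information". Where VI.E mentions a key, for archived samples, the key ties the code to identifying information about the participant.

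On allocation, VI.B.3 says that a random sequence generator "will be used to determine the order by which each participant will undergo the two trials". It does not say who holds the resulting list or from whom it is kept. VI.D.3 confirms that each person receives both breads: "If the participant was assigned WWB in Trial 1, WB will be assigned in Trial 2".

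The protocol does not state that participants, dietitian, clinic staff, laboratory analysts or the statistician are blinded to the bread. The only use of the word blind is in the title of a cited earlier study.

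**The concern.** VI.F presents a confidentiality measure as a control on measurement bias. A code limits treatment-related bias only if the person making a judgement cannot tell which bread a sample or record belongs to. VI.F does not say that this is so for anyone.

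The trial's main contrast is the within-person difference between the WWB and WB endpoints, compared between high- and low-responders. The expected directions are set out in advance in section III. If staff who know the bread make discretionary choices, those choices can lean towards the expected result. The choice with most leverage is who counts as a responder. Section III gives an expectation (a fall of more than 25%) and VI.B.3 gives expected group sizes (6-12 high and 5-10 low of 40), but neither is a fixed rule. Section IV allows HOMA-IR, endotoxin and inflammatory markers to be added to the definition if glycemic response alone does not yield enough of each group.

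**Working it through.** There is no plan figure to reproduce, and masking does not depend on alpha, power or sample size. The check sets the sections side by side.

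1. **What the code distinguishes.** It is one number per participant (VI.F, VI.E). Under the crossover (VI.D.3) that number is the same in the WWB and WB periods. It therefore separates people, not breads. No period-specific or bread-specific code is described.

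2. **What the code-break sentence can mean.** There are two readings.
   - *Participant identity.* The analysis can run as planned, but the delay gives no protection against treatment-related bias.
   - *Bread order.* The mixed model needs diet as a fixed factor (VI.B.3), the main contrast is WWB against WB (VI.B.3), and high-responders are described by a fall on WWB relative to WB (section III). None of this can be completed with bread order hidden unless files carry neutral A/B labels, and even then the directional responder rule needs the labels revealed. No such labelling is described.

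   The first reading fits the rest of the protocol better.

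3. **Dietary records.** These are named in the VI.F claim. Under VI.C.5, staff weigh returned food and compute nutrient intake, and the diets are identical between arms except for the bread. The assessor has the food in hand and needs the bread type for the calculation. Masking is implausible here, whatever the code.

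4. **Laboratory assays.** A tube marked with participant number and period does not show the bread. An analyst without the order list would be masked in effect. The protocol neither arranges this nor rules it out. The alkylresorcinol assay (VI.C.8) is a special case, because it is planned as a marker of WWB intake and may reveal the bread.

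5. **Who is exposed.** Test meals are eaten at the centre four days a week (VI.C.5). Participants are monitored at visits by the PI, a postdoctoral scholar or a graduate student (VI.G). The PI also verifies the analysis (VI.F). No independent key holder is named.

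6. **Reach.** With all 40 participants completing:
   - Serum and fecal metabolomics visits: 40 × 2 arms × 2 days (1 and 14) = 160.
   - Glucose tolerance tests: 40 × 2 arms × 1 day (14) = 80.
   - Of the 160 metabolomics visits, the 40 on day 1 of the first period precede any study bread.

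   These counts show how many visits the safeguard would have to cover. They do not measure bias.

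**The case against.** The strongest reply is that VI.F does delay code-breaking until the analysis is verified, and that order is randomised per participant, so a coded tube tells an analyst nothing about the bread unless that analyst has the order list. This stands in part. A reader might infer that a participant number cannot hide the bread in a crossover, or that no protection exists. The documents do not support either inference for assays. They are silent on who holds the list, and silence supports only that masking is not established.

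Three other stronger readings also fail:

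- VI.D.2 says "All samples will be coded to maintain participant anonymity", which might suggest that anonymity is the only purpose of all coding. That sentence concerns the screening draw, taken before any bread is assigned.
- VI.E makes the participant number available to research personnel. It does not say that they have the bread-order list.
- One might infer that a single small team feeds participants, runs assays and analyses data. The protocol describes partly separate functions: bread-making in Food Science and Technology, a registered dietitian, a separate biochemical laboratory, and a biostatistician in Biomedical Informatics. Overlap is documented only in part, chiefly through the PI. That the breads look different is a reasonable inference, but it is not stated.

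It is also fair to say that OGTT glucose is read by a clinical assay, so knowing the bread has little room to move it. A responder rule fixed in advance would remove much of the discretion even without masking. The second point bears on the remedy, but the protocol fixes no such rule.

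**Conclusion.** The concern holds in a limited form. The code described in VI.F is an identity code shared by both breads, and the code-break sentence does not establish that bread order is concealed. Protection against treatment-related bias is not established for assays and analysis, and is implausible for dietary records.

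No size can be given, because the documents contain nothing from which to compute a bias. Instrument-read outcomes such as glucose are little exposed. The main exposure is the open responder definition, which drives the primary comparison, followed by feature filtering and annotation in the metabolomics. The protocol gives no filtering rules; that such choices will arise is an assumption from the nature of untargeted work.

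The conclusion also assumes that no concealment procedure is set out in a document outside this protocol. It does not show that any result will be biased. The change is worth making because it is cheap and protects the choice on which the main comparison rests.

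**What to change.** 1. Label every aliquot with a random specimen number that carries no participant, period or bread information before it goes to assay.
2. Name an existing team member outside assay and analysis to hold the order key and the specimen link.
3. Release analysis files with the breads as A and B, used consistently across participants so that the mixed model can run. Withhold alkylresorcinol results until lock, since they can undo the labels.
4. Lock quality control, feature filters and a written responder rule, including whether and how the section IV markers enter it. Then unmask and apply the directional rule.
5. Reword VI.F to claim masking of assay and analysis staff only, not of dietary records, and to state that the codes broken at the end are the bread-order codes.

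The cost is a relabelling step and a key to manage, with no extra samples or staff. Masking stays incomplete for whoever runs the alkylresorcinol assay, and VI.F should say so.
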